PECS/SAP blocks with liposomal bupivacaine improve the Overall Benefit Analgesia Score averaged over the postoperative days 1, 2, and 3. A 20% reduction in OBAS geometric mean, a-priori, was defined as minimal clinically important difference.

Secondary hypotheses:

- (1) PECS/SAP blocks decrease postoperative cumulative opioid consumption over the initial three postoperative days.
- (2) PECS/SAP blocks improve pulmonary mechanics, on each of the postoperative days 1, 2 and 3, from the baseline.

Exploratory Hypothesis:

- (1) PECS/SAP blocks improve the Quality-of-Recovery score averaged over the postoperative days 1 and 3, with a difference of 8 points being considered the minimum clinically important difference.⁵⁴
- (2) PECSII and SAP blocks reduce persistent postoperative surgical pain

Methods

The study will be conducted at the Cleveland Clinic Main Campus with IRB approval and written informed consent from participating patients.

Inclusion Criteria

1. 18-85 years old;
2. Elective MICS for isolated robotically-assisted mitral valve repair via anterolateral thoracotomy approach.

Exclusion Criteria

1. Weight less than 50 kg;
2. Pregnancy or lactation;
3. Emergency surgery and patients transferred from the ICU to the operating room;
4. Redo cardiothoracic surgery or post-operative reoperation within 72 hours of index procedure (including minor chest wall procedures including tube thoracostomy, thoracentesis or percutaneous drain placement);
5. Anticipated endotracheal intubation > 24 hours;
6. Anticipated non-study nerve block that provides analgesia to the intercostal nerves;
7. Active systemic or cardiopulmonary infection;
8. Mechanical circulatory support;
9. Allergy or contraindication to study local anesthetics;
10. Current chronic pain or routine opioid use (patients on chronic enteral opioids like Percocet or Vicodin) in a dose of > 30 mg of morphine-milligram-equivalents for at least 10 days in last 30 days;
11. Poorly controlled psychiatric disorders;
12. Clinically important current neurologic deficit; e.g. spinal cord injury, paralysis of extremity, any neurologic deficit in the region of the block
13. Active liver disease or cirrhosis;
14. Pacemaker generator or breast implants ipsilateral to surgery;
15. Previous participation in this study.
16. eGFR <30 or chronic kidney disease

Study protocol

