Liposomal bupivacaine dosing is not weight-based and the full 266-mg bottle can be administered to adult thoracic patients. A maximum of 150 mg bupivacaine HCL can be mixed with Exparel. This equates to one 30-mL bottle of 0.5% bupivacaine HCL or two (2) bottles of 0.25% bupivacaine HCL. If a higher volume of the local anesthetic is needed a 10 ml of normal saline can be added to the mixture of bupivacaine HCL and liposomal bupivacaine. Thus patients ≥ 60 kg will receive 150 mg of bupivacaine HCL, while patients weighing < 60 kg need to have the bupivacaine dose calculated but can still receive full 20 ml of Exparel.

Patients randomized to standard analgesia technique will be given parenteral opioids (such as fentanyl or hydromorphone) until they are converted to the enteral medications such as Percocet.

Study Measurements

Patent demographics will be collected from preoperative interviews and chart review (Table 1). Cumulative opioid consumption, non-opioid analgesics, and length of stay will be

captured electronically using Epic and/or PHDS. Other secondary and descriptive outcome data as well as surgical and intraoperative data will be collected prospectively (Table 2).

Data will be obtained from the following sources: The Society of Thoracic Surgeons (STS) database, Cardiovascular Information Registry (CVIR) of the Heart and Vascular Center at the Cleveland Clinic, the electronic medical record (EPIC), and the electronic Anesthesia Record Keeping System (ARKS).

a) OBAS score

The OBAS score questionnaire (Table 3) will be obtained and score calculated by the research team on post-operative days 1-3. We will calculate the average of the OBAS scores obtained. The OBAS score is a validated postoperatively calculated, multi-dimensional questionnaire that consists of 7 items (Table 3) encompassing not only scale-rated pain score but different aspects of analgesia benefits, side effects and overall patient's satisfaction.⁵³

The OBAS score is based on 7 questions and ranges from 0 to 28 points that will be administered on POD 1 – POD 3. Although these are longitudinal ordinal data, we will be able to treat OBAS scores as continuous data in the analyses with the lower score correlating with better resolution of the analgesia treatment. A 20% reduction in OBAS geometric mean, a-priori, was defined as minimal clinically important difference..^{57,58}

b) Pain assessments

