The Blood samples will be collected into K2EDTA tubes and will be centrifuged at 1000 to 1200g for 10 min to obtain plasma within 1 hour of collection. After centrifugation, the plasma will be transferred into polypropylene tubes. The plasma samples will be stored frozen at -20°C or colder until shipment. All samples will be shipped frozen with dry ice to ABS Laboratories, Inc. The shipment address is as follows: [name] ABS Laboratories, Ltd. [name]

Descriptive and Safety Outcomes

- a) Total ICU length of stay;
- b) Hospital length of stay;
- c) Cumulative non-opioid analgesics included acetaminophen, ketorolac, ibuprofen, gabapentin, and pregabalin will be recorded and compared over the initial three postoperative days;
- d) Anxiolytics such as alprazolam, lorazepam, and diazepam will be recorded and compared.

Statistical analysis

We will compare groups on potentially confounding demographic and preoperative risk factors listed in Table 1 using appropriate summary statistics (i.e., mean ± standard deviation, median [Q1, Q3], or N (%) as appropriate) as well as surgical and intraoperative data will be collected prospectively (Table 2). Randomized groups will be compared on balance on these characteristics using absolute standardized difference, defined as the absolute difference in means, mean ranks, or proportions divided by the pooled standard deviation.

Analyses will be modified intent-to-treat, including all randomized patients who received PECSII/serratus blocks (regardless of whether it's consistent with the randomization).

We will summarize descriptive and safety outcomes by randomized groups using appropriate summary statistics (i.e., mean \pm standard deviation, median [Q1, Q3], or N (%) as appropriate). No statistical tests will be performed on these outcomes.

We will use an alpha of 0.05 for both the primary and secondary analyses, with a significance criterion of 0.05 for the primary analysis and 0.0167 for each secondary analysis (i.e., 0.05/3, Bonferroni correction). Analyses will be completed using SAS version 9.4 or newer (SAS Institute, Carey, North Carolina) or R version 3.2.4 or newer (R Project for Statistical Computing, Vienna, Austria).

Primary analysis

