We will estimate the PECS/SAP blocks effect on OBAS scores using a repeated measures linear regression model with an autoregressive correlation structure, adjusting for ALL imbalanced confounders (if any). Based on these model we would be able to claim if the PECS/SAP blocks had any effect on the OBAS score compared to standard routine analgesia during any of the postoperative time up to third postoperative day. Due to non-normality of OBAS score, it will be log-transformed for analysis. We will report model based P-value and the geometric mean ratio for OBAS scores along with confidence intervals. To assess whether the PECS/SAP blocks effect is heterogeneous over three postop days, we will assess the treatment-by-time interaction using a significance criterion of 0.20. If it appears that the treatment effect is heterogeneous, we will report the treatment effect separately for each postoperative day POD 1, POD 2 and POD 3 using a Bonferroni correction as appropriate (e.g., 0.05/3; 3 postoperative days).

Secondary Analysis

Morphine equivalents will be calculated based on the conversions specified in Table 4 below. Total opioid consumption as well as intraoperative and postoperative day 1, 2, and 3 totals will be collected and converted to milligram morphine equivalents. Patients will not be provided opioid patches for pain relief because there is no known conversion to morphine equivalents. Cumulative opioid consumption data is typically right skewed, so we will normalize it for analyses using a log transformation. Opioid consumption will be reported separately for postoperative day (POD) 0 after surgery, POD 1, POD2, and POD3. We will estimate the effect of PECS/SAP blocks to standard routine analgesia on log cumulative opioid consumption using a repeated measures linear regression model with an autoregressive correlation structure, adjusting for any imbalanced baseline or surgical characteristics between groups.

To assess whether the effect of PECS/SAP blocks is heterogeneous over time, we will assess the treatment-by-time interaction using a significance criterion of 0.20. If it appears that the treatment effect is heterogeneous, we will report the treatment effect separately for each postoperative day using a Bonferroni correction as appropriate (e.g., 0.05/3; 3 postoperative days).

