Comps-Pulm-Pneumonia Indicate whether the patient had Pneumonia diagnosed by any of the following: positive cultures of sputum, transtracheal fluid, bronchial washings, and/or clinical findings consistent with the diagnosis of pneumonia. May include chest X-ray diagnostic of pulmonary infiltrates
Comps-Pulm-Vent Prol Indicate whether the patient had Pulmonary Insufficiency requiring ventilator. Include (but not limited to) causes such as ARDS and pulmonary edema and/or any patient requiring mechanical

ventilation > 24 hours postoperatively
Comps-Other-GI Comps
Indicate whether the patient had a postoperative occurrence of any GI complication including:

 a. GI bleeding requiring transfusion b. pancreatitis with abnormal amylase/lipase requiring nasogastric (NG) suction therapy c. cholecystitis requiring cholecystectomy or drainage d. mesenteric ischemia requiring exploration e. other GI complication

Table 3: OBAS score – To calculate the OBAS score, obtain sum of scores in questions 1–6 and add ‘4 minus score in question 7’.

1	Please rate your current pain at rest	0 minimal pain, 1 mild pain, 2 moderate pain, 3 severe pain, and 4 maximum imaginable pain
2	Please grade any distress and bother from vomiting in the past 24 h	0 = not at all to 4 = very much
3	Please grade any distress and bother from itching in the past 24 h	0 = not at all to 4 = very much
4	Please grade any distress and bother from sweating in the past 24 h	0 = not at all to 4 = very much
5	Please grade any distress and bother from freezing in the past 24 h	0 = not at all to 4 = very much
6	Please grade any distress and bother from dizziness in the past 24 h	0 = not at all to 4 = very much
7	How satisfied are you with your pain treatment during the past 24 h	0 = not at all to 4 = very much

Table 4: Morphine Equivalent Conversion Table

Agent	PO (mg)	IV (mg)

Morphine	30	10
Hydromorphone	7.5	1.5
Fentanyl	-	0.1
Oxycodone	20	-
Hydrocodone	30	-

Table 4: Surgical, intraoperative and postoperative data

Time on CPB
X-clamp time
RBCs
Plt
FFP
Cryo
Inotropes in the OR
Time to extubation
Length of ICU stay
Length of hospital stay
Intraoperative ultrasound record and image of fascial plain blocks (SAP and PECS)

References

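### The primary analysis takes the log of daily OBAS but gives no rule for scores of zero, which is the best attainable score, so the geometric mean ratio depends on an unstated choice

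*Combined protocol and SAP*

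**What the plan says.** Under Primary analysis, the block effect on OBAS is estimated "using a repeated measures linear regression model with an autoregressive correlation structure, adjusting for ALL imbalanced confounders". Then: "Due to non-normality of OBAS score, it will be log-transformed for analysis". The result is given as a ratio: "We will report model based P-value and the geometric mean ratio for OBAS scores along with confidence intervals". The section also tests whether the effect differs across the three postoperative days and, if it does, reports each day separately.

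Under Study Measurements, item a): "The OBAS score is based on 7 questions and ranges from 0 to 28 points", "with the lower score correlating with better resolution of the analgesia treatment". The scoring rule is in Table 3: "To calculate the OBAS score, obtain sum of scores in questions" 1 to 6, then add 4 minus the satisfaction item.

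The Primary hypothesis section sets the yardstick on the ratio scale: "A 20% reduction in OBAS geometric mean, a-priori, was defined as minimal clinically important difference". Sample Size Considerations plans for a true geometric mean ratio of 0.80.

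Nowhere do the documents give an added constant, a rule for zero scores or an alternative model. Two places point to a different unit of analysis: the Primary hypothesis and the OBAS paragraph of Study Measurements both speak of a score averaged over days 1 to 3.

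**The concern.** A logarithm cannot be taken of zero, and here zero is the result the block is meant to produce. The plan cannot be executed on such days without a decision it does not contain, and each obvious decision changes what is estimated.

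- **Zero days drop out.** SAS sets the log of zero to missing, so the best days leave the model. If the block works, more are lost from the block arm and the estimate is pulled towards 1. R, which the plan also allows, returns minus infinity, so the analyst must intervene.
- **A constant c is added.** The model then estimates a ratio for OBAS + c. The 20% difference and the planned 0.80 are ratios of OBAS itself, so the two cannot be compared directly.

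At stake are the primary estimate, its reading against the 20% difference and, if zeros are common, power. The log scale came in with Version 6, after enrolment had begun, which is a further reason not to leave the choice open.

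**Working it through.** **1. Zero is attainable.** From Table 3: pain 0, five side-effect items at 0, satisfaction 4. Score = 0 + 5 × 0 + (4 − 4) = 0.

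**2. The planned sample size.** Inputs from Sample Size Considerations: ratio 0.80, CV 50%, alpha 0.05 (taken as two-sided), power 90%.
- Log-scale SD = √ln(1 + 0.5²) = 0.4724; effect = |ln 0.80| = 0.2231.
- n per group = 2 × (1.960 + 1.282)² × 0.4724² / 0.2231² ≈ 94.2, so 95. The t-based version gives 96 per group, 192 in total, which is the plan's figure.

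The figure reproduces. It treats the outcome as strictly positive and lognormal, with no allowance for zeros.

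**3. Effect of a constant with no zeros at all.** For a control score m, a 20% reduction on the OBAS + 1 scale is (0.8m + 1)/(m + 1):
- m = 2: 2.6/3 = 0.87
- m = 3: 3.4/4 = 0.85
- m = 4: 4.2/5 = 0.84
- m = 6: 5.8/7 = 0.83

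Read against 0.80, a true 20% reduction would look like 13-17%.

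**4. Illustration with zeros.** The documents give no OBAS mean or zero frequency, so everything here is assumed: three Poisson days per patient with a lognormal patient effect, scores capped at 28, block mean 0.8 times control mean, 400,000 simulated patients per arm. The patient log-SD is 0.3, except 0 at mean 4. If the stated CV were an OBAS CV, means 4-6 would fit it as a daily figure (simulated 50-54%) and means 2-3 as a three-day-average figure (simulated 45-51%).

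| Control mean | Zero days, control vs block | Zeros dropped | OBAS + 1 | OBAS + 0.5 |
|---|---|---|---|---|
| 4-6 | 1-2% vs 2-4% | 0.80-0.81 | 0.82-0.83 | 0.80 |
| 3 | 7% vs 11% | 0.84 | 0.85 | 0.81 |
| 2 | 16% vs 22% | 0.88 | 0.87 | 0.83 |

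As a benchmark, with almost no zeros (mean 6, log-SD 0) dropping gives 0.79. The difference between a ratio of means and a geometric mean ratio therefore accounts for only about 0.01.

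**5. Power.** 98 per arm, 6,000 trials, patient-clustered robust variance, critical value 1.975 from Table A, interim looks ignored, log-SD 0.3.

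| Control mean | Zeros dropped | OBAS + 1 | Ratio of means |
|---|---|---|---|
| 2 | about 65% | 81% | 83% |
| 3 | 82-84% | 90% | 91% |
| 6 | 97% | 97% | 98% |

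**6. If the three-day average is logged.** A zero then needs three zero days. In the same model at means 2-3, zero averages occur in 0.1-0.8% of controls and 0.3-1.8% of block patients. Dropping them gives 0.79-0.80.

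**The case against.** The strongest reply is that the practical effect may be nil. At control means of 4-6 dropping zeros hardly moves the estimate, and if the averaged score is what gets logged, zeros almost vanish. Both statements are correct. The first cannot be relied on, because the documents do not say where OBAS scores lie. The second does not fit the Primary analysis section: an autoregressive structure and a treatment-by-time interaction need one score per day. It does show that the unit of analysis should be stated.

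A second reply is that the calibration is soft. This stands. Sample Size Considerations does not say that its CV is for OBAS, nor for which time unit, so matching scenarios to it is an assumption.

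A third is that a constant is no cleaner. This also stands in part: at means 4-6, adding 1 moves the ratio further from 0.80 than dropping does, and the re-expressed 20% difference depends on a control score not yet known. The case for a constant is that it keeps every patient-day and is fixed in advance, not that it recovers the OBAS ratio.

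A reader might infer four stronger things that the documents do not support:
- **That the ratio could be wildly wrong.** In this model a constant of 0.01 gives 0.64-0.75, but nothing in the documents suggests so small a constant for an integer score from 0 to 28.
- **That the choice decides success by moving the estimate across 0.80.** Superiority is judged "with a significance criterion of 0.05 for the primary analysis" and by the Table A boundaries; 0.80 is a benchmark for interpretation.
- **That the sample size is wrong because of this gap.** The figure reproduces from its own inputs.
- **That zeros are common, or that they never matter for opioid totals.** No frequency is given for either outcome.

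**Conclusion.** The gap is real. The primary model, read as it stands, cannot be run on a day with the best possible score, and the unstated remedy determines what the reported ratio means. That conclusion rests on the text alone.

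The size is illustrative only. Under the assumed distribution with a true mean ratio of 0.80, dropping zeros is trivial at control means 4-6 (0.80-0.81) and material at means 2-3 (0.84-0.88). At those lower means, power is about 65-82% with zeros dropped and 81-90% with OBAS + 1. If the three-day average were logged, the bias would be negligible.

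This should be fixed because the remedy is cheap and the estimate is the primary one. It is not evidence that the trial's result is biased.

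**What to change.** Before unblinded analysis, amend the Primary analysis section to:
- state that daily scores are modelled, that zeros are retained, and the one constant used, for example log(OBAS + 1);
- label the result as a ratio of OBAS + c and not read it directly against 0.80. With c = 1, a 20% reduction corresponds to about (0.8m + 1)/(m + 1), with m the observed control score. The formula can be fixed now; its value cannot;
- report the number of zero days per arm;
- add one zero-retaining sensitivity analysis on untransformed daily OBAS, for example a log-link GEE with robust standard errors, giving a ratio of means.

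Apply the same rule to any interim analysis still to come (looks were planned at 66 and 132 patients, and the documents do not say whether they have taken place) and to the log opioid totals under Secondary Analysis wherever a total is zero.

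The cost is a short amendment and one extra analysis, with no new data. The shifted ratio lies somewhat closer to 1 (0.82-0.87 in the scenarios above). At control means 2-3 and 6, adding 1 costs about 1-2 percentage points of power against a ratio of means.

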Consent will be obtained at least a day before surgery. Patients will be randomized the day of surgery upon presentation to the operating room to either a *treatment group* (PECS/SAP blocks) or a *control group* (standard parenteral analgesia technique with or without incisional LA infiltration) using secure web-based randomization. Randomization will be stratified by aortic or mitral valve surgery, with random blocking in each case. The system will be accessed shortly

before surgery to conceal allocation as long as possible. Clinicians will not be blinded to the intervention, but all outcomes will be assessed by research personnel who are blinded to the group assignment.

Anesthetic and Surgical Management

Anesthetic care will be performed as usual for Cleveland Clinic cardiothoracic surgical procedures. This includes use of standard ASA monitors and may include the use of arterial or central venous pressure monitoring, trans-esophageal echocardiography, and lung isolation using a bronchial blocker or a double lumen endotracheal tube. Medication administration for induction and maintenance of anesthesia will also be consistent with usual care and will include intravenous opioids such as fentanyl and hydromorphone. Intravenous lidocaine will not be administered upon induction of anesthesia.

Pressure-control ventilation will be used with a tidal volume not exceeding 6-10 ml/kg ideal body weight during two- and one-lung ventilation. Fluids will be managed conservatively per routine. Patients not extubated at the end of the procedure will be sedated with propofol. Surgical procedures with the assistance of the cardio-pulmonary bypass will be performed in their usual manner. The general approach for the AV replacement will be via the right anterior thoracotomy in the 3rd intercostal space.⁴ The MV repair/replacement procedures will be approached via the right lateral thoracotomy inframammary incision in the 4th intercostal space in the mid-axillary line and augmented, as needed, with the stab incisions for the robotic ports.⁴

Chest Wall Analgesia

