The anatomic basis for chest wall analgesia has been described in detail previously.^{31-33,49} We describe the conduct of the blocks as used for MICS procedures at our institution. The patients randomized to the “blocks” will receive PECS II and serratus anterior for the MVR requiring antero-lateral thoracotomy and port incisions. The PECS/serratus blocks will be performed with the patient under the general anesthesia before incision. If proves impossible to perform blocks preoperatively because of surgical urgency, they will be done at end of surgery.

PECS II blocks:

Patients will be positioned supine, and prepped and draped in a sterile fashion. An ultrasound probe will be placed just below the clavicle in the mid-clavicular line.

For the PECS II block, the probe will be scanned inferiorly and laterally until the plane between the pectoralis minor and serratus muscle is identified. The serratus muscle can be clearly seen coursing over the ribs, while the intercostal muscles are seen in the interspaces between the ribs. Once the plane is identified the needle is again advanced in an “in-plane” fashion. Once the needle location is confirmed by normal saline hydro-dissection, a 20-30 ml of local anesthetic solution is administered into the space.

Serratus plane block:

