We also plan for two interim analyses at 1/3 and 2/3 of the planned enrollment to assess safety, feasibility and formal efficacy and futility. Therefore, interim adjusted sample size is N=98 patients per group, or N=196 total. We will use the conservative gamma spending function with parameters -5 and -5 for alpha (efficacy) and beta (futility), respectively. If the alternative hypothesis is true (the treatment effect exists) there will be a cumulative probability of 10%, 53% and 100% of crossing either an efficacy or futility boundary at the 1st, 2d and final analyses, respectively (Table A and Figure 1 below contains boundary Information). Planned first and second interim analyses will be performed upon accrual of 66 and 132 patients respectively. **Therefore, planned number of patients for the analysis is N=98 patients per group, or N=196 total.**

We will also enroll at least 5 pilot patients in the beginning of the study to test the feasibility of protocol adherence and data collection.

Table A. Boundary Information for interim analysis (3 analyses = 3 stages):

Boundary Information (Standardized Z Scale)**Null Reference = 0**

Stage	Information Level	Alternative		Boundary Values				
		Reference	Lower	Lower	Upper	Beta	Beta	
	Proportion	Lower	Upper	Alpha	Beta	Beta	Alpha	
1		0.3333	-1.88730	1.88730	-3.18319	-0.02167	0.02167	3.18319
2		0.6667	-2.66904	2.66904	-2.64022	-0.53609	0.53609	2.64022
3		1.0000	-3.26890	3.26890	-1.97517	-1.97517	1.97517	1.97517

Figure 1. Boundary plot

[figure not shown]

Table 1: Patient demographic and preoperative risk factors

Sex
Age (years)
Surgery Type (Robot MVR, thoracotomy MVR, AVR through RAT)
Coronary Artery Disease
Hypertension
Pervious Myocardial infarction
Peripheral Arterial Disease
Previous vascular surgery
Smoker (current or former)
Cerebrovascular disease
Diabetes mellitus

Renal failure: Indicate whether the patient has 1) a documented history of renal failure and/or 2) a history of creatinine > 2.0. Prior renal transplant patients are not included as pre-op renal failure unless since transplantation their creatinine has been or currently is > 2.0.
Left ventricular EF

Table 2: Surgical, intraoperative and postoperative data

Time on CPB
X-clamp time
RBCs
Plt
FFP
Cryo
Inotropes in the OR
Time to extubation
Length of ICU stay
Length of hospital stay

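### The opioid model's covariate rule admits surgical variables recorded after randomization, which exposes that estimate to bias, though the documents do not show that bias occurs

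*Combined protocol and SAP*

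**What the plan says.** The opioid model in the Secondary Analysis section is a repeated measures regression on log cumulative consumption, "adjusting for any imbalanced baseline or surgical characteristics between groups". The wording sets surgical characteristics beside baseline ones as a second class, and it cites no table.

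On timing, the Study protocol section says: "Patients will be randomized the day of surgery upon presentation to the operating room". Chest Wall Analgesia adds: "The PECS/serratus blocks will be performed with the patient under the general anesthesia before incision". If that proves impossible, the block is done at the end of surgery. On conduct, "Clinicians will not be blinded to the intervention", while Anesthetic and Surgical Management says "Anesthetic care will be performed as usual".

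The opening paragraph of Statistical analysis names the preoperative risk factors of Table 1 and, in the same sentence, the surgical and intraoperative data of Table 2. Its next sentence applies the absolute standardized difference to the characteristics just named. No cut-off for imbalance is given. The table in question is headed "Table 2: Surgical, intraoperative and postoperative data".

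The OBAS model adjusts for imbalanced confounders, if any. The spirometry models adjust for the baseline lung values and, again, for imbalanced confounders.

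**The concern.** A covariate measured before randomization cannot be changed by the assigned arm, so adjusting for it leaves the treatment effect intact. A covariate measured afterwards carries no such guarantee. If allocation changes it and it is related to opioid use, the adjusted coefficient is no longer the total effect of assignment, and the error can go in either direction.

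Choosing covariates by observed imbalance makes this worse, because an item that allocation has moved is more likely to look imbalanced than one it has not. Cumulative opioid consumption is secondary hypothesis 1 and is tested at a Bonferroni level, so both the estimate and its error rate are at stake.

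**Working it through.** **Which variables the rule reaches.** Table 1 is preoperative. Every Table 2 item is recorded after randomization: bypass time, clamp time, four blood products, operating-room inotropes, time to extubation, lengths of stay and complications. The balance paragraph covers both tables, and the opioid sentence then draws on imbalanced baseline or surgical items. The seven intraoperative items are the most plausible ones to be admitted.

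**Inputs.** The plan states no figure on this point. From Sample Size Considerations: 98 per arm. The 96 per arm before interim adjustment reproduces: with ln 0.80 = −0.2231 and log SD √ln(1 + 0.5²) = 0.4724, the normal formula gives 95 and the noncentral t gives 96. Significance levels are 0.05/3 = 0.0167 (Statistical analysis) and 0.05/4 = 0.0125 (the four outcomes in Secondary Analysis), so both are shown. Everything else is assumed: the shift *d* of one admitted item by allocation, its correlation *r* with log opioid use, the imbalance cut-off and the opioid CV.

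**Selection.** The SE of a standardized difference is √(2/98) = 0.143. The probability of being flagged is:

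| Cut-off | No shift | Shift 0.3 SD |
|---|---|---|
| 0.10 | 0.48 | 0.92 |
| 0.20 | 0.16 | 0.76 |

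**Bias and false positives.** Suppose the block has no effect on opioid use, and the item is linked to opioid use only through patient factors. Then bias = −(*d* × *r*), in SD units, and SE = √(1 − *r*²) × 0.143 × √(1 + *d*²/4). Two-sided rejection uses z = 2.394 (0.0167) or 2.498 (0.0125).

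| *d* / absolute *r* | Size of bias (SD) | SE | Rejection at 0.0167 | Rejection at 0.0125 |
|---|---|---|---|---|
| 0.1 / 0.1 | 0.010 | 0.142 | 0.017 | 0.013 |
| 0.1 / 0.3 | 0.030 | 0.136 | 0.019 | 0.015 |
| 0.2 / 0.2 | 0.040 | 0.141 | 0.021 | 0.016 |
| 0.2 / 0.3 | 0.060 | 0.137 | 0.028 | 0.021 |
| 0.3 / 0.3 | 0.090 | 0.138 | 0.042 | 0.033 |
| 0.3 / 0.5 | 0.150 | 0.125 | 0.116 | 0.097 |

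These treat the item as always admitted and use one value per patient, which simplifies the planned repeated measures model. Simulating adjustment only when the item is flagged (10,000 runs, 0.3/0.3, cut-off 0.10 or 0.20) gives a mean bias of 0.08 to 0.09 SD and rejection of 0.034 to 0.044 at the 0.0167 level. With no shift, the mean estimate is 0.00 and rejection 0.013 to 0.016.

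**On the ratio scale.** The geometric mean ratio is multiplied by exp(± bias × s), with s = √ln(1 + CV²): 0.472 at CV 50% and 0.833 at CV 100%. A bias of 0.06 gives 0.97 or 1.03 at CV 50%, and 0.95 or 1.05 at CV 100%. A bias of 0.15 gives 0.93 or 1.07, and 0.88 or 1.13.

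**Masking a real effect.** Suppose the true ratio is 0.80, the block lowers the item by 0.2 to 0.4 SD, and each SD of the item adds 0.1 to 0.2 to log opioid use. The adjusted ratio then runs from 0.80 × exp(0.02) = 0.82 to 0.80 × exp(0.08) = 0.87.

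**The case against.** The strongest reply is that no mechanism is documented. Anesthetic care is as usual, surgery is done in its usual manner, and the Introduction says that these blocks do not cause a sympathectomy. Bypass time, clamp time and transfusion may well be untouched by a chest wall block, and without a shift there is no bias. This stands, and it sets the limit of the point. Lack of blinding leaves room for care to differ by arm but does not show that it does.

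Second, the term *surgical characteristics* is undefined, and Table 1 contains one preoperative surgical item, Surgery Type. A reader might infer from the inclusion criterion ("Elective MICS for isolated robotically-assisted mitral valve repair via anterolateral thoracotomy approach") that this item is constant, so that the phrase can only mean Table 2. That goes too far. The version history says the criterion was put in clearer words only in Version 6, Anesthetic and Surgical Management still describes repair or replacement with robotic ports as needed, and Table 1 still lists three surgery types. The case for Table 2 rests instead on the balance paragraph, and on the fact that a preoperative item would already count as baseline.

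Third, the larger figures need inputs at the top of an assumed range. This also stands: 0.116 requires both maxima, and the middle of the grid gives 0.019 to 0.028 against a nominal 0.0167.

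Fourth, a reader might infer that the primary OBAS analysis has the same defect. Its wording is open to that reading through the balance paragraph, but that paragraph attaches the idea of confounding to Table 1, which is the more natural meaning. For OBAS and spirometry this is a matter of clarification.

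**Conclusion.** The point holds for the opioid model as written: its covariate rule lets variables recorded after randomization into a confirmatory secondary test, and picks them in a way that favours those changed by allocation. It does not establish that the opioid estimate is biased. The size is unknown, because the documents give no effect of the block on any Table 2 item, no opioid CV and no planned opioid effect. The calculated range runs from negligible to material and rests entirely on the assumed shift and correlation.

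A reader might also infer that imbalance-triggered adjustment is itself biased and that a fixed covariate list is required. That does not follow. Within Table 1, chance imbalance leaves the covariate set dependent on the data but does not bias the effect.

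The change should be made because it removes the exposure at almost no cost. Confidence is medium, mainly because the key term is undefined.

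**What to change.** Delete *or surgical* from the opioid model. State once, for all models, that covariates come only from the preoperative variables of Table 1, plus the baseline lung value in the spirometry models. This also settles what imbalanced confounders means for OBAS and spirometry. Report Table 2 by arm descriptively, and label any model that adjusts for a Table 2 item as a sensitivity analysis.

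Whether Table 1 covariates are fixed in advance or chosen on imbalance is the sponsor's choice. If imbalance is kept as the trigger, stating the cut-off would make the rule reproducible.

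The change is to wording only and needs no new data. Its one drawback is that a chance imbalance in an intraoperative item is then handled only in the sensitivity analysis.
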